
20.1 Criteria for Suspending/Terminating a Study Center

Boston Scientific reserves the right to stop the inclusion of subjects at a study center at any time after the study initiation visit if no subjects have been enrolled for a period beyond 12 months after center initiation, or if the center has multiple or severe protocol violations/noncompliance without justification and/or fails to follow remedial actions.

In the event of termination of investigator participation, all study devices and testing equipment, as applicable, will be returned to BSC unless this action would jeopardize the rights, safety or well-being of the subjects. The IRB/EC and regulatory authorities, as applicable, should be notified. All subjects enrolled in the study at the center will continue to be followed for the protocol follow-up period after study termination. The Principal Investigator at the center must make provision for these follow-up visits unless BSC notifies the investigational center otherwise.

21 Publication Policy

In accordance with the Corporate Policy on the Conduct of Human Subject Research, BSC requires disclosure of its involvement as a sponsor or financial supporter in any publication or presentation relating to a BSC study or its results. In accordance with the Corporate Policy for the Conduct of Human Subject Research, BSC will submit study results for publication (regardless of study outcome) following the conclusion or termination of the study. Boston Scientific adheres to the Contributorship Criteria set forth in the Uniform Requirements of the International Committee of Medical Journal Editors (ICMJE; <http://www.icmje.org>). In order to ensure the public disclosure of study results in a timely manner, while maintaining an unbiased presentation of study outcomes, BSC personnel may assist authors and investigators in publication preparation provided the following guidelines are followed.

- All authorship and contributorship requirements as described above must be followed.
- BSC involvement in the publication preparation and the BSC Publication Policy should be discussed with the Coordinating Principal Investigator(s) and/or Executive/Steering Committee at the onset of the project.
- The First and Senior authors are the primary drivers of decisions regarding publication content, review, approval, and submission.

CFR	Code of Federal Regulations
CRF	Case Report Form
CRO	Contract Research Organization
CT	Computerized Tomography
EC	Ethics Committee
eCRF	Electronic Case Report Form
EDC	Electronic Data Capture
ERCP	Endoscopic Retrograde Cholangiopancreatography
EUS	Endoscopic Ultrasound
EUS-GBD	Endoscopic Ultrasound Gallbladder Drainage
FDA	Food and Drug Administration
GB	Gallbladder
GCP	Good Clinical Practice
GI	Gastrointestinal
Hb	Hemoglobin
ICF	Informed Consent Form

ICH	International Conference on Harmonisation of Technical Requirements for Registration of Pharmaceuticals for Human Use
ICMJE	International Committee of Medical Journal Editors
ICU	Intensive Care Unit
IDE	Investigational Device Exemption
IRB	Institutional Review Board
ISO	International Organization for Standardization
ITT	Intent-To-Treat
LAMS	Lumen-Apposing Metal Stents
PC	Percutaneous Cholecystostomy
PT-GBD	Percutaneous Gallbladder Drainage
PG	Performance Goal
PP	Per-Protocol
SADE	Serious Adverse Device Event
SAE	Serious Adverse Events
SEMS	Self-Expanding Metal Stents
UADE	Unanticipated Adverse Device Effect
USADE	Unanticipated Serious Adverse Device Effect

24 Appendices

24.1 AXIOS™ EUS-GBD with Comparison to PC (Windbladh et al 2009)

	1st Author, Year	# of Patients	30 Day Mortality (%)	Biliary/ Procedure Mortality (%)	Technical Success	Clinical Success
Axios	Itoi et al 2012 [22]	5	0/5 (0%)	0/5 (0%)	5/5 (100%)	5/5 (100%)
	de la Serna-Higuera et al 2013 [18]	13	0/13 (0%)	0/13 (0%)	11/13 (85%)	11/11 (100%)
	Walter et al 2016 [16]	30	5/30 (17%)	4/30 (13.3%)	27/30 (90%)	26/27 (96%)
	Irani et al 2015 [4]	15	2/15 (13%)	0/15 (0%)	14/15 (93%)	15/15 (100%)
	Law et al 2016 [21]	7	3/7 (42%)	0/7 (0%)	7/7 (100%)	7/7 (100%)
	Kahaleh et al 2016 [23]	15	0/15 (0%)	0/15 (0%)	13/15 (87%)	13/15 (87%)
	Irani et al 2017 [19]	45	23/45 (51%)	1/45 (2.2%)	44/45 (96%)	43/45 (96%)
	Dollhopf et al 2017 [20]	75	7/75 (9%)	0/75 (0%)	74/75 (98.7%)	71/74 (95.9%)
	Teoh et al 2017** [17]	59	1/38 (1.7%)*	1/38 (1.7%)*	57/59 (96.6%)	53/59 (89.8%)
	Axios Total	264	41/243	6/243	252/264	244/264
Axios Average	264	16.9%	3.0%	95.5%	92.4%	
PC	Average PC Rates [6]	1870	15.4%	4.0%	98.9%	86.0%
Axios vs PC	Axios vs PC Fisher' Exact p-value		0.57	0.37	0.0002	0.003

** Of 59 patients in Teoh et al 2017, 21 were already reported in Walter et al 2015, procedure mortality and 30-day mortality represents the 38 cases of Teoh 2017 that were not reported in Walter 2015

*Teoh et al 2017: Procedure Mortality – 2 cases (1 overlaps with Walter et al 2015; 1 (Aspiration Pneumonia)

24.2 EUS-GBD VS. PCGBD

1st Author, Year	# subjects EUS-GBD	# subjects PCGBD	Technical Success EUS-GBD	Technical Success PCGBD	Clinical Success EUS-GBD	Clinical Success PCGBD	# AE's EUS-GBD	# AE's PCGBD
Irani et al 2017 [19]	45	45	44/45 (97.8%)	45/45 (100.0%)	43/45 (95.6%)	41/45 (91.1%)	8/45 (17.8%)	14/45 (31.1%)
Teoh et al 2017 [17]	59	59	57/59 (96.6%)	59/59 (100.0%)	53/59 (89.8%)	56/59 (94.9%)	19/59 (32.2%)	44/59 (74.6%)
Tyberg et al 2016 [41]	42	113	40/42 (95.2%)	112/113 (99.1%)	40/42 (95.2%)	97/113 (85.8%)	9/42 (21.4%)	24/113 (21.2%)
Average	146	217	96.6%	99.5%	93.2%	89.4%	24.7%	37.8%

1st Author, Year	30 Day Mortality EUS-GBD	30 Day Mortality PCGBD	Procedure Mortality EUS-GBD	Procedure Mortality PCGBD	No. of subjects w/add'l interventions EUS-GBD	No. of subjects w/add'l interventions PCGBD	Overall Complications EUS-GBD	Overall Complications PCGBD
Irani et al 2017 [19]	23/45 (51.1%)	20/45 (44.4%)	1/45 (2.2%)	3/45 (6.7%)	3/45 (6.7%)	45/45 (100.0%)	8/45 (17.8%)	14/45 (31.1%)
Teoh et al 2017 [17]	5/59 (8.5%)	1/59 (1.7%)	2/59 (5.1%)	0/59 (0.0%)	NR	NR	19/59 (32.2%)	44/59 (74.6%)
Tyberg et al 2016 [41]	0/42 (0.0%)	4/113 (3.5%)	NR	NR	4/42 (9.5%)	28/113 (24.8%)	9/42 (21.4%)	24/113 (21.1%)
Average	19.2%	11.5%	2.9%	2.9%	8.0%	46.2%	24.7%	37.8%

1. PROTOCOL SUMMARY

Objective(s)	To evaluate the safety and effectiveness of the AXIOS™ Stent with Electrocautery Enhanced Delivery System in the management of symptoms of acute cholecystitis as an alternative to percutaneous gallbladder drainage. It is anticipated that a transluminal EUS drainage approach with the AXIOS™ stent will provide benefits in time to resolution of acute cholecystitis as well as a lower the fraction of patients whom would require additional interventions compared to those treated with percutaneous cholecystostomy; study endpoints will be used to further evaluate.
Test Device	AXIOS™ Stent and Electrocautery Enhanced Delivery System
Control Device	None
Study Design	Prospective, single arm, multi-center trial
Planned Number of Subjects	30
Planned Number of Investigational Sites	Up to 7 centers (US and OUS)
Primary Endpoints	
Primary Effectiveness Endpoint:
 
Time to resolution of acute cholecystitis measured in days.
 
Note: Resolution is defined as either a fever of less than 100.5°F, or at least a 4-point decrease in the pain score, or WBC count less than 12,000/cc, with improvement in at least two of these categories without the deterioration of the third category.
 
Secondary Effectiveness Endpoint:
 
Rate of re-interventions including but not limited to stent migration, stent occlusion by gallbladder stones, and luminal debridement.

Additional Endpoints	
 1. Stent patency (ability to facilitate gallbladder drainage) defined indirectly as resolution of acute cholecystitis or, in the absence of resolution of acute cholecystitis, endoscopic observation of unobstructed AXIOS™ stent lumen 2. Technical stent placement success: Successful stent placement, defined as transmural placement of the AXIOS™ stent with confirmed stent patency via (i) drainage visualized through the stent or fluoroscopically,

	
or (ii) ability to endoscopically observe the inner walls of the gallbladder through the AXIOS™ stent
 
3. Technical stent removal success: Successful stent removal, defined as ability to remove the AXIOS™ stent endoscopically without stent removal related serious adverse events4. Rate of recurrence of acute cholecystitis and its management5. Number of cumulative hospital and ICU days from initial stent placement to resolution of symptoms of acute cholecystitis
--	--

2. INTRODUCTION

This statistical plan addresses the planned analyses for the Axios Gallbladder Drainage IDE Study based on protocol # 92147168. Specified analyses may be used for scientific presentations and/or manuscripts and may not all be provided to Regulatory Authorities.

IMPORTANT NOTE: This SAP documents changes to the Statistical Methods outlined in the protocol. This SAP shall be following where there are any differences between the Statistical Methods in the protocol and this SAP. *Differences to the Statistical Methods between the protocol and this SAP will be in bold, italics.*

3. ENDPOINT ANALYSIS

3.1 Primary Effectiveness Endpoint

The primary effectiveness endpoint is the time to resolution of acute cholecystitis measured in days.

Note: Resolution is defined as either a fever of less than 100.5°F, or at least a 4-point decrease in the pain score, or WBC count less than 12,000/cc, with improvement in at least two of these categories without the deterioration of the third category.

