	
indwelling indefinitely): stent removal, adverse event/device event assessment, documentation of any re-intervention (as applicable), stent patency assessment, clinical symptom assessment, current medication(s)
 
Note: After stent removal, the physician will continue to treat the patient per standard of practice
 
 • 72 Hour Post-Stent Removal Visit (+24 hours) (Telephone): adverse event assessment, documentation of any re-intervention (as applicable), current medication(s) • End of Study Visit (Office/Hospital Visit): at 30 days (+/- 7 days) post stent removal or 90 days (+/- 14 days) post stent placement (whichever comes first) for patients with an AXIOS™ stent implanted; 30 days post-resolution of cholecystitis or 60 days post-index procedure (whichever comes first) for patients without an AXIOS™ stent implanted: clinical symptom assessment, laboratory markers of inflammation or cholestasis, adverse event assessment, documentation of any re-intervention (as applicable), current medications • Additional visits as needed: Adverse events assessment / device event assessment, imaging (as applicable), labs (as applicable), documentation of any re-intervention (as applicable), current medication
Study Duration	Subjects will be on study for up to 15 weeks
Key Inclusion Criteria	
 1. Patient requiring intervention for the management of symptoms associated with acute cholecystitis 2. Patients referred for percutaneous drainage of the gallbladder who are not surgical candidates because of advanced age, anesthetic risk, significant co-morbidities and/or overall health 3. Eligible for endoscopic intervention 4. Acute Cholecystitis (AC) Grade I (mild) or II (moderate) per Tokyo guidelines [3]: 
 • AC Grade I (mild) defined as acute cholecystitis in an otherwise healthy patient with mild local inflammatory changes and without organ dysfunction. Criteria for grade II or III not met. • AC Grade II (moderate) defined by any one of the following characteristics 
 ○ Leukocytosis (>18,000 cells per mm³) ○ Palpable, tender mass in right upper quadrant ○ Symptom duration >72 hours

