4.1 Primary Effectiveness Endpoint

The primary effectiveness endpoint is time to resolution of acute cholecystitis which will be measured in days. Resolution is defined as either a fever of less than 100.5°F, or at least a 4-point decrease in the pain score, or WBC count less than 12,000/cc, with improvement in at least two of these categories without the deterioration of the third category.

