3.1.1 Hypothesis

The analysis of the primary effectiveness endpoint is to compare the days to clinical resolution using an AXIOS™ stent to a performance goal (PG).

The null and alternative hypotheses for the primary effectiveness endpoint analysis are as follows:

$$H_0: \mu_{\text{days}} \geq \text{PG}$$

$$H_1: \mu_{\text{days}} < \text{PG}$$

where μ_{days} is the mean days to clinical resolution for patients in the AXIOS™ Gallbladder Drainage Study and PG is a performance goal of 3.5 days based on a literature review of percutaneous drainage studies.

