3.1.2 Sample Size Calculation

This analysis of the primary effectiveness endpoint is to compare the observed days to clinical resolution for AXIOS™ stents from this study to a PG.

- Expected AXIOS™ stent (test) mean days to clinical resolution = 2.35 days with standard deviation 2 days (point estimate of days to clinical resolution based on historical rates reported in literature [1] with median days to clinical response of 1 day, range 0 to 3 days)
- PG = 3.5 days (mean days to resolution for percutaneous gallbladder (GB) drainage (PC-GBD) based on historical rates reported in literature [2])
- Test significance level (α) = **0.025** (1-sided)
- Power (1- β) = **82%**
- Evaluable number of patients needed = 27
- Expected rate of attrition = 10%
- Enrolled number of patients = 30

The historical time to cholecystitis resolutions comes from 2 studies that report time to cholecystitis for endoscopic ultrasound-guided transmural gallbladder drainage (EUS-GBD) [1] and PC-GBD [2] (Table 3.1-1).

Table 3.1-1. Time to Cholecystitis Resolution (in days)

Reference	EUS-GBD	PC-GBD
Irani (2015) [1]	Median=1 (0-3) [N=15]	N/A
Kedia (2015) [2]	N/A*	Mean 4.6 [N=43]

* Endoscopic drainage was not transmural and therefore was not included in the analysis

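### The white cell limit in the primary endpoint is given per cc; read literally it is 1,500-fold below the protocol's own leukocytosis limit, very likely a unit slip for mm³

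*SAP*

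**What the plan says.** The primary endpoint is time to resolution in days. Resolution rests on three categories: temperature, pain score and WBC count. The WBC limit is "WBC count less than 12,000/cc" in Protocol section 4.1. The same number and unit appear in the Protocol synopsis, SAP section 1 and SAP section 3.1, where the text runs "or WBC count less than 12,000/cc, with improvement in at least two of these categories". The combining rule reads "with improvement in at least two of these categories without the deterioration of the third category".

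Inclusion criterion 4 (Protocol synopsis and section 5.1) puts a patient in Grade II if any one of several findings is present. One of them is "Leukocytosis (>18,000 cells per mm³".

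Neither document defines cc, converts between the two units or states a reporting unit for WBC. The laboratory lists in Protocol section 7.4 name WBC without a unit.

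**The concern.** A cc and a mm³ differ by a factor of 1,000, so the entry criterion and the endpoint limit are not on the same scale as written. The number 12,000 makes sense beside 18,000 only if both are per mm³.

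The limit helps to set each patient's resolution date. Those dates feed the Kaplan-Meier mean that is tested against the 3.5-day performance goal (SAP section 3.1.3). Under SAP section 3.1.3, a stented patient who does not resolve is censored and does not count as a success. The planned margin between the expected mean and the goal is only 3.5 − 2.35 = 1.15 days, so the dating rule should not depend on how a reader repairs a unit.

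The trial runs at US and non-US sites. The documents describe no central laboratory and no endpoint adjudication at which the unit would be settled; the independent review board in Protocol section 15 has a safety role.

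**Working it through.** **Inputs**
- Endpoint limit: below 12,000 per cc (Protocol synopsis and 4.1; SAP 1 and 3.1).
- Grade II limit: above 18,000 cells per mm³ (Protocol synopsis and 5.1, inclusion criterion 4).
- Design values in SAP 3.1.2: "mean days to clinical resolution = 2.35 days with standard deviation 2 days", goal 3.5 days, "Evaluable number of patients needed = 27", attrition 10%, one-sided alpha 0.025, power 82%. Protocol 8.1 has alpha 0.022 and power 80.4%.

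**Step 1. Reproduce the plan's own figures.** One-sample, one-sided t-test by the noncentral t distribution:
- Difference = 3.5 − 2.35 = 1.15 days; SD = 2; n = 27.
- Noncentrality = (1.15 / 2) × √27 = 2.99.
- Power = 82.0% at alpha 0.025 and 80.4% at alpha 0.022. Both agree with the documents.
- Enrolment = 27 / (1 − 0.10) = 30, also as stated.

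No WBC value enters these formulas, so the unit cannot change them.

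**Step 2. Convert the limits.** 1 cc = 1 cm³ = 1,000 mm³.

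| Limit | per mm³ | per cc | ×10⁹/L |
|---|---|---|---|
| Endpoint, as written | 12 | 12,000 | 0.012 |
| Endpoint, if meant per mm³ | 12,000 | 12,000,000 | 12.0 |
| Grade II leukocytosis, as written | 18,000 | 18,000,000 | 18.0 |

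**Step 3. Compare.**
- As written: 18,000 / 12 = 1,500.
- Both per mm³: 18,000 / 12,000 = 1.5.
- The two readings of the endpoint limit differ by 12,000 / 12 = 1,000.

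**Step 4. Follow the literal reading through the rule.** Three categories give three pairs: fever with pain, fever with WBC, and pain with WBC. Suppose improvement means crossing the stated limit. Two of the three pairs then need a count below 12 cells/mm³, which is not realistic in these patients. The remaining route is fever with pain, provided that WBC does not deteriorate. If any fall in WBC counts as improvement, all three pairs stay open and the literal limit blocks nothing. The text does not say which of these is meant.

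**The case against.** The strongest reply is that nobody would apply a limit of 12 cells/mm³. The protocol's grading criterion shows the intended scale, and a site or programmer who met the literal figure would notice that it makes no clinical sense. General data review and queries are also planned (Protocol 8.4 and 9.1; SAP 4.3). Most of this stands, and it is why the likely effect on collected data is small. It does not make the text correct. If the analysis uses 12,000 per mm³ while both documents say per cc, the derivation departs from the written definition of the primary endpoint. The planned queries are not specific to this unit.

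A reader might infer that the WBC category can never be met, or that every patient's endpoint is wrong by a factor of 1,000. The documents do not support either inference. Improvement is not defined as crossing the limit, and resolution remains reachable through fever and pain. The factor of 1,000 describes the unit; it is not an effect on resolution times. Nothing in the documents shows how many patients would depend on WBC.

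Nor is this an evident route to false success. Applied literally, the limit would mainly delay or remove resolutions, which would tend to lengthen the estimated mean and work against the claim.

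**Conclusion.** The unit is wrong as written, or at least irreconcilable with inclusion criterion 4, in all four statements of the primary endpoint. The conversion is exact: 12 cells/mm³, which is 1,500-fold below the Grade II limit, against a ratio of 1.5 if both are per mm³. That this is a slip of cc for mm³ is an inference from the matching scale of the two numbers. It is very likely, but it is for the sponsor to confirm.

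The practical effect is probably small. This rests on two assumptions: that sites read the number per mm³, and that improvement is not applied strictly as crossing the literal limit. If both fail, a two-limit resolution would need fever and pain together, and some patients would be dated later or censored. The documents give no basis for saying how many. The 27 evaluable patients, 30 enrolled and 82% power are unchanged. The point deserves correction because it concerns a decision limit in the primary endpoint, not because it threatens the design.

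**What to change.** 1. The sponsor confirms the intended unit and reconciles it with inclusion criterion 4. If 12,000 cells per mm³ is the intended value, that is 12.0 × 10⁹/L.
2. Correct SAP sections 1 and 3.1 now, and the Protocol synopsis and section 4.1 at the next amendment. SAP section 2 asks for departures from the protocol's statistical methods to be marked, so the SAP correction should be flagged in the same way until the protocol catches up.
3. State in the SAP that every WBC value is converted to the confirmed unit before the resolution date is derived.

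The SAP correction is one line plus a conversion step in the endpoint program. The protocol wording carries a real cost, because Protocol section 13.3 requires IRB/EC review of any amendment. Holding it for the next planned amendment limits that cost. The sample size need not be revisited.

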3.1.1 Hypothesis

The analysis of the primary effectiveness endpoint is to compare the days to clinical resolution using an AXIOS™ stent to a performance goal (PG).

The null and alternative hypotheses for the primary effectiveness endpoint analysis are as follows:

$$H_0: \mu_{\text{days}} \geq \text{PG}$$

$$H_1: \mu_{\text{days}} < \text{PG}$$

where μ_{days} is the mean days to clinical resolution for patients in the AXIOS™ Gallbladder Drainage Study and PG is a performance goal of 3.5 days based on a literature review of percutaneous drainage studies.

3.1.2 Sample Size Calculation

This analysis of the primary effectiveness endpoint is to compare the observed days to clinical resolution for AXIOS™ stents from this study to a PG.

- Expected AXIOS™ stent (test) mean days to clinical resolution = 2.35 days with standard deviation 2 days (point estimate of days to clinical resolution based on historical rates reported in literature [1] with median days to clinical response of 1 day, range 0 to 3 days)
- PG = 3.5 days (mean days to resolution for percutaneous gallbladder (GB) drainage (PC-GBD) based on historical rates reported in literature [2])
- Test significance level (α) = **0.025** (1-sided)
- Power (1- β) = **82%**
- Evaluable number of patients needed = 27
- Expected rate of attrition = 10%
- Enrolled number of patients = 30

The historical time to cholecystitis resolutions comes from 2 studies that report time to cholecystitis for endoscopic ultrasound-guided transmural gallbladder drainage (EUS-GBD) [1] and PC-GBD [2] (Table 3.1-1).

Table 3.1-1. Time to Cholecystitis Resolution (in days)

Reference	EUS-GBD	PC-GBD
Irani (2015) [1]	Median=1 (0-3) [N=15]	N/A
Kedia (2015) [2]	N/A*	Mean 4.6 [N=43]

* Endoscopic drainage was not transmural and therefore was not included in the analysis

3.1.3 Analysis

The primary effectiveness endpoint will be evaluated for all ITT patients regardless of whether an AXIOS™ stent is implanted. Patients for whom an AXIOS™ stent is implanted and cholecystitis is resolved will be considered a success for the endpoint and the days to resolution will be the date of resolution minus the date of the index procedure. If a patient does not receive an AXIOS™ stent, the patient will be considered a failure for the endpoint with censoring at 60 days. If a subject receiving an AXIOS™ stent does not achieve resolution of cholecystitis for any reason, the patient will be treated as censored in the Kaplan-Meier analysis and the days to censoring will be the date of censoring minus the date of the index procedure. The date of censoring will be the earliest of the following:

- date of the patient receiving a cholecystectomy,
- date of the patient dying,
- date of last contact for patients who withdraw from the study or are lost to follow-up, or
- date of the AXIOS™ stent removal.

The mean time to resolution and standard error of the mean will be estimated from a Kaplan-Meier analysis so that subjects for whom resolution is not obtained can be included in the analysis.

The estimated mean, $\hat{\mu}_T$, from the Kaplan-Meier analysis will be calculated as:

$$\hat{\mu}_T = \int_0^T \hat{S}(t)dt$$

where $\hat{S}(t)$ is the estimated survival function from the Kaplan-Meier analysis and T is time of longest days to resolution or days to censoring. The variance of $\hat{\mu}_T$, $\hat{V}(\hat{\mu}_T)$, is estimated as:

$$\hat{V}(\hat{\mu}_T) = \sum_{i=1}^D \left[\int_{t_i}^T \hat{S}(t)dt \right]^2 \frac{d_i}{Y_i(Y_i - d_i)}$$

where D is the number of distinct times (days to resolution), t_i is the i-th time, Y_i is the number of patients at risk at time t_i , and d_i is the number of events at time t_i . The $100(1 - \alpha)\%$ upper bound of the confidence interval of the mean will be calculated as:

$$\hat{\mu}_T + Z_{1-\alpha} \sqrt{\hat{V}(\hat{\mu}_T)}$$

For the primary effectiveness endpoint of days to clinical resolution, testing will be performed as described below.

The estimated mean and standard error from the Kaplan-Meier analysis will be used to construct a one-sided **97.5%** upper confidence bound of the mean. If the upper **97.5%** confidence bound of the mean days to clinical resolution for the AXIOS™ group is less than the performance goal of 3.5 days, the null hypothesis will be rejected in favor of the alternative hypothesis and the mean days to resolution for the AXIOS™ group will be considered to be significantly less than the performance goal of 3.5 days.

As a worst-case scenario sensitivity analysis, the Kaplan-Meier analysis for the primary effectiveness endpoint will be re-analyzed with 60 days as the time to censoring for all censored patients with time to censoring <60 days.

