- *If placement of the AXIOS™ stent is attempted but no stent placement occurs, patient will be followed until 30 days after resolution of the cholecystitis, or 60 days after the index procedure, whichever comes first. The patient's treatment will be at the discretion of the physician.*

Additional Notes:

- *In case of leakage of gallbladder contents resulting from inability to place the AXIOS™ stent after puncturing the gallbladder, a second attempt will be made by placing a needle through the original enteric puncture and re-accessing the gallbladder. Once a guidewire is placed, a new AXIOS™ stent would be placed. If a second attempt to place an AXIOS™ stent is not successful, transpapillary gallbladder drainage with a cystic duct stent or percutaneous drainage may also be considered. Endoscopic closure of the*

- puncture site in the duodenal wall or stomach wall using conventional endoscopic techniques is advised in case of complete misdeployment and loss of puncture site access.
- In addition, percutaneous drainage of any fluid collection caused by the bile leak might be needed. If endoscopic and percutaneous approaches for the management of the gallbladder leak are unsuccessful, then surgery should be considered as soon as possible in order to avoid uncontrolled biliary peritonitis. Patients who receive an AXIOS™ stent and experience a procedural complication during stent placement will be followed until end of study, which is 30 days post stent removal or 90 days post stent placement (whichever comes first).
 - In case of leakage of gallbladder or GI tract contents causing inflammation or peritonitis after the AXIOS™ placement procedure, due to early stent migration or other causes the following complication management approaches should be considered in the following sequence:
 - Administration of antibiotics and monitoring of the patient
 - Endoscopic management (e.g. ERCP)
 - Percutaneous drainage
 - Surgical closure of the leak and gallbladder drainage
 - In case of AXIOS™ stent misplacement or migration, stent will be removed endoscopically.

A CT scan with contrast (unless contraindicated) will be required in all of the above-mentioned circumstances.

- The maximum stent indwell time of 30 to 60 days should be intended. This timeframe takes into consideration both the time needed for AC resolution as well as time needed for fistula formation, unless medically recommended.

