The primary effectiveness endpoint will be evaluated for all ITT patients regardless of whether an AXIOS™ stent is implanted. Patients for whom an AXIOS™ stent is implanted and cholecystitis is resolved will be considered a success for the endpoint and the days to resolution will be the date of resolution minus the date of the index procedure. If a patient does not receive an AXIOS™ stent, the patient will be considered a failure for the endpoint with censoring at 60 days. If a subject receiving an AXIOS™ stent does not achieve resolution of cholecystitis for any reason, the patient will be treated as censored in the Kaplan-Meier analysis and the days to censoring will be the date of censoring minus the date of the index procedure. The date of censoring will be the earliest of the following:

- date of the patient receiving a cholecystectomy,
- date of the patient dying,
- date of last contact for patients who withdraw from the study or are lost to follow-up, or
- date of the AXIOS™ stent removal.

Success Criteria for the Primary Effectiveness Endpoint:

For the primary effectiveness endpoint of days to clinical resolution, testing will be performed as described below.

The mean time to resolution and standard error of the mean will be estimated from a Kaplan-Meier analysis so that subjects for whom resolution is not obtained can be included in the analysis.

The estimated mean and standard error from the Kaplan-Meier analysis will be used to construct a one-sided 97.8% upper confidence bound of the mean. If the upper 97.8% confidence bound of the mean days to clinical resolution for the AXIOS™ group is less than the performance goal of 3.5 days, the null hypothesis will be rejected in favor of the alternative hypothesis and the mean days to resolution for the AXIOS™ group will be considered to be significantly less than the performance goal of 3.5 days.

As a worst-case scenario sensitivity analysis, the Kaplan-Meier analysis for the primary effectiveness endpoint will be re-analyzed with 60 days as the time to censoring for all censored patients with time to censoring <60 days.

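### For a stented patient, resolution reached only after rescue gallbladder drainage scores as an AXIOS success, and no planned analysis shows how far the primary result depends on such rescue

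*SAP*

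**What the plan says.** **Scoring.** SAP 3.1.3 and protocol 8.1 use the same rule. For a stented patient who resolves: "Patients for whom an AXIOS™ stent is implanted and cholecystitis is resolved will be considered a success for the endpoint", timed from the index procedure to resolution. For a stented patient who does not: "If a subject receiving an AXIOS™ stent does not achieve resolution of cholecystitis for any reason, the patient will be treated as censored", at the earliest of cholecystectomy, death, last contact or stent removal. For a patient without a stent: "If a patient does not receive an AXIOS™ stent, the patient will be considered a failure for the endpoint with censoring at 60 days". Rescue drainage appears nowhere in the rule.

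**Rescue.** Among the additional notes in protocol 7.4, for leakage that causes inflammation or peritonitis after placement, the "following complication management approaches should be considered in the following sequence". The list runs from antibiotics through endoscopic management and percutaneous drainage to surgery.

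**Checks.** The worst-case analysis moves censored patients to day 60. The tipping-point analysis of the secondary endpoint covers patients who neither resolved nor had a re-intervention. The Treated and Per Protocol cohorts are defined by implantation and eligibility. The secondary endpoint compares the re-intervention rate with 46.2%, and SAP 3.3 requires both endpoints to succeed. SAP section 2 gives the SAP precedence over the protocol's statistical methods.

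**The concern.** The objective is to evaluate AXIOS as an alternative to percutaneous drainage, and the test is against a percutaneous benchmark. Take two patients who are drained percutaneously on day 2 and resolve on day 5. If the first has a stent that did not do its job, the score is success at 5 days. If the stent could not be placed in the second, the score is failure at 60 days. The plan thus withholds credit for rescue after failed placement but gives it after failed function, and states no reason.

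A resolution that AXIOS did not produce can therefore help AXIOS beat the percutaneous goal. The reader of the report would not see this, because neither sensitivity analysis nor any alternative cohort removes or re-times such a patient. With 30 patients and no control arm, a few can matter. A scoring rule chosen after rescues are known would be open to the criticism of being post hoc.

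**Working it through.** **1. The plan's own power.** Inputs from SAP 3.1.2: "mean days to clinical resolution = 2.35 days with standard deviation 2 days", "PG = 3.5 days (mean days to resolution for percutaneous gallbladder (GB) drainage", "Evaluable number of patients needed = 27". Noncentrality = (3.5 − 2.35)/2 × √27 = 2.99. A one-sided one-sample t-test has power 82.0% at 0.025 (stated: 82%) and 80.4% at the protocol's 0.022. Both reproduce. Neither allows for patients scored at 60 days.

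**2. How many rescues the secondary endpoint tolerates.** Exact binomial against 46.2%, assuming that rescue counts as a re-intervention:

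| Re-interventions | One-sided P | Clopper-Pearson upper bound | Result |
|---|---|---|---|
| 8/30, alpha 0.025 | 0.0231 | 45.9% | pass |
| 9/30, alpha 0.025 | 0.0536 | 49.4% | fail |
| 6/30, alpha 0.003 | 0.0027 | 45.9% | pass |
| 7/30, alpha 0.003 | 0.0086 | 49.6% | fail |

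With only 27 evaluable patients the SAP ceiling is 6 (7/27: P = 0.0255).

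**3. The primary endpoint with 8 rescues.** Assumed data: 11 patients resolve on day 1, 11 on day 2, and 8 on day 5 after rescue. SAP 3.1.3 formulas, n = 30, Z = 1.96.

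- *As written.* S = 1, then 19/30 from day 1, then 8/30 from day 2. Mean = 1 + 0.6333 + 3 × 0.2667 = 2.43. Variance = 1.4333² × 11/(30 × 19) + 0.8² × 11/(19 × 8) = 0.0860 (the day-5 term has no remaining area and is taken as zero). SE = 0.293, bound = 3.01. Pass. Nobody is censored, so the worst-case analysis gives the same result.
- *The 8 held to day 60.* Mean = 1 + 0.6333 + 58 × 0.2667 = 17.10, SE = 4.72, bound = 26.36. Fail.
- *The 8 censored at rescue on day 2.* The curve ends at day 2. Mean = 1 + 0.6333 = 1.63, bound = 1.81. Censoring at rescue improves the result.

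**4. One rescue.** Assumed: 14 resolve on day 1, 15 on day 2, 1 on day 5 after rescue. As written: mean 1.63, bound 1.92. Held to day 60: mean = 1 + 0.5333 + 58 × 0.0333 = 3.47, bound 7.23. Even if the other 29 resolve on day 0, mean = 60/30 = 2.00, SE = √(2² × 29/(30 × 1)) = 1.966 and bound = 5.85, above 3.5.

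**5. Dependence on the other 22 patients (8 rescued, scored as written).**

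| Assumed pattern of the other 22 | Latest rescue day that passes | One day later |
|---|---|---|
| 0–3 days, median 1, mean 1.14 | day 6 (mean 2.43, bound 3.25) | bound 3.67, fail |
| Planning values: mean 2.36, SD about 2, gamma shape | day 4 (mean 2.80, bound 3.46) | bound 3.81, fail |

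**The case against.** The strongest defence is that the two endpoints divide the work: time to resolution counts however it is reached, and further procedures count in the secondary. That is a coherent treatment-policy approach. Delay from rescue also raises the mean, because the clock starts at the index procedure. Protocol 1.1 describes percutaneous drainage itself as needing repeated re-interventions before resolution, so the historical times may include such patients, and a 60-day penalty on the AXIOS side could create its own imbalance. This stands as an argument against imposing the 60-day rule as primary. It does not explain why unstented patients are scored differently, nor does it supply the missing sensitivity analysis.

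A reader might also infer three stronger things that the documents do not support:

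- *That the protocol expects crossover to percutaneous gallbladder drainage.* The list in 7.4 is contingent on leakage and starts with antibiotics. Its entry does not say that the gallbladder is what is drained, and the preceding note speaks of draining a fluid collection.
- *That a trial with 8 rescues is a realistic success.* At the planned 8.0% re-intervention rate, the probability of 8 or more among 30 is 0.2%. If the other 22 follow the planning mean, rescues resolving on day 5 fail the primary.
- *That resolution after stent removal or cholecystectomy certainly counts as success.* Both dates are in the censoring list, which suggests that resolution should come first, but the success sentence sets no such limit. The text is ambiguous.

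**Conclusion.** The concern holds as a gap in scoring and in sensitivity analysis. As written, rescue-driven resolution in a stented patient is an AXIOS success, the same course without a stent is a 60-day failure, and no planned analysis shows the difference. The secondary endpoint bounds the problem only loosely, at 8 of 30 under the governing SAP alpha (6 of 30 under the protocol's 0.003). That ceiling requires all 30 to be stented, no other re-intervention, and rescued patients resolving by about day 4 to 6, depending on the others. If rescue is not counted as a re-intervention, which the open-ended definition leaves unstated, there is no ceiling.

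The result is sensitive even to one patient: a bound of 1.92 days as written against 7.23 held to day 60. Most of that jump comes from the 60-day convention, so it shows how much the scoring choice matters and is not an estimate of bias. The day patterns are assumptions; the documents give no rate of percutaneous rescue after successful placement.

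The documents do not establish that the 60-day rule must be the primary analysis. That is the sponsor's estimand choice. The point concerns scoring only, not when rescue should be given.

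**What to change.** 1. In SAP 3.1.3 and protocol 8.1, state how resolution after non-AXIOS gallbladder drainage, cholecystectomy or stent removal is scored, and reconcile the success sentence with the censoring list.
2. Extend the worst-case analysis: set stented patients who resolve only after such rescue to 60 days, as for unstented patients. Do not simply censor at the rescue date, which lowers the mean (2.43 to 1.63 days in the example).
3. Report the proportion of ITT patients resolved on AXIOS alone, with an exact interval. In the example it is 22/30 = 73.3%, where the present rule shows 30/30.
4. State in SAP 3.2 that such rescue counts as a re-intervention.

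**Cost.** Wording and one further sensitivity run. Re-intervention documentation is already scheduled from the daily visits to the end of study (protocol 7.1). The downside is a less favourable sensitivity result if rescue occurs.

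If the sponsor makes the 60-day rule primary, the 82% power must be recalculated, because one rescue alone fails the test. With an assumed rescue probability of 1% to 3% per patient, the chance of at least one in 30 is 1 − 0.99³⁰ = 26% to 1 − 0.97³⁰ = 60%, so power could not exceed 74% to 40%.
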